7.2.2 Troubleshooting Visits

The logs will have detailed information on attempts made to troubleshoot device issues. All tech team members will follow the troubleshooting flow chart for offline devices and devices with low battery

- **Action Plans:**

- Offline devices - If the device is offline for more than 48 hours and is still offline for next day, the tech team member who is in charge for respective ID will plan for a troubleshooting visit as per participant's convenience. The troubleshooting visit needs to be completed within the next 24 hours.
- Low battery devices – If the device's battery status falls below 20% (or depending on the situation, like low network strength) the tech team will plan for a troubleshooting visit within the next 12 hours.

- **Planning visit**

- Schedule coordination with Assessment Coordinator. For devices offline more than 48 hours despite problem-solving with the participant over the phone, Tech Team member contacts Tech Team Coordinator for further action. For male participants, the tech team coordinator overseeing setting up of the visit. However, for female participants, the tech team coordinator contacts the Assessment Coordinator for help coordinating the visit, since it requires the presence of a female interviewer.
- Scheduled visit: The tech team member will call the participant to schedule a troubleshooting visit.
- Planning unscheduled visit: If the team is not able to establish contact with the participant over the phone via primary number or secondary number and if the participant has given permission for tracking visit, a tracking visit will be conducted. As an alternative plan, the tech team members will give the ID to the Assessment Coordinator to find out the participant's next ART Visit date and track accordingly.
- The troubleshooting plan will then be updated in the daily log.

- **Conducting troubleshooting visit:**

- For a scheduled visit, the tech team members will call and confirm before meeting the participant.
- Checklist of items to be carried for Troubleshooting visit
 - Tool kit
 - Diagnostic Box
 - Tablet

- OTG (On the Go device which is used to read the SD card data and copy onto the tablet devices)
- Fevibond
- Extra 2 new device,
- SIM(Vodafone/Idea)
- Power Bank (only carried during troubleshooting visits)
- Troubleshoot register book
- 3M tape

c. Troubleshooting the device- The following procedure will be carried out by the Tech Team member during the troubleshoot of the device.

- Check the device if it is on ON/OFF mode.
- Restart the device (3 times)
- Check if the device is damaged
 - Check the device for outside damages like, locking system, sensor, reed switch holder, battery etc.,
 - If any part of the device is damaged, change the box (during this process team member should call the Project Engineer and update the status.
 - The damaged box will be returned to the Project Engineer the same day.
- Check for network issues (offline devices only)
 - Shift participant device SIM into diagnostic box to check the network status. If the device is still offline then change the network.
 - If the device is still showing offline, change the box (during this process team member should call the Project Engineer and update the status.
 - If the device is still showing offline mode team will plan to collect SD Card data once in a month and follow up calls should be made once a week to restart the device. This message will be communicated to the participant.
- Changing the battery (low battery devices only)
 - If the battery in the device has been drained out to non-charging, change the battery (during this process team member should call the Project Engineer and update the status.
 - The old battery has to be returned to the Project Engineer the same day. The Project Engineer will charge the battery to 100% in the office and re-use the same for another device.

d. Before concluding the troubleshooting visit, SD Card data will be collected, and the team member will note down the details of the visit in the trouble shooting field log book and get the participant to sign as acknowledgment.

e. Once the troubleshooting visit is completed, the tech team member will communicate on the Whatsapp group with a short report and a screen shot of the website's dashboard once it is online/charged. The tech team member will leave the site only after the device is online on the dashboard and/or charged and approved by the Project Engineer.

f. After a troubleshoot at office or on site, the tech team member who conducted the troubleshoot will update the troubleshoot log with all the details of the troubleshoot conducted. This document has to be updated on the same day. The document is reviewed by the Tech coordinator and data associate on a daily basis.

- g. Possession of study devices : B the End of the day The Tech team members will handover the devices, tablet and power bank to the Data team.
- h. The troubleshooting report needs to be updated in the troubleshoot log by end of day or next day by 10.00.am

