1.4 Randomization To Intervention Or Control Arm

At the completion of baseline (see 2.3 for details), participants will be randomized to intervention or control arm. At each site, half of the participants will form the intervention group and the remaining participants will form the control group. The UCSF statistician will use a random number generator (<https://www.randomizer.org/>) to randomly pick half of the 60 ID numbers from one site and put them into one group. The 30 non-chosen numbers will form a second group, The statistician will then randomly decide which group will be assigned to the control group and which one to the intervention group. The process will be repeated for the other site.

This randomized set of ID numbers will be shared with the intervention team (tech team) at each site and they will assign the next available ID on the list, thereby randomizing the participant, at the time of completion of baseline. The tech team will prepare the TMB device according to the intervention arm allocated and give the participant the TMB device (see section 7.1.4 for details below). The assessment team will be blinded to the allocation.

SECTION 2: ASSESSMENT: BASELINE AND FOLLOW-UP

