2.3.3. Handing Out The TMB Device

All participants will receive a TMB device during the baseline interview session. The participants assigned to the intervention group will meet with intervention team member (tech team) to go over their pill taking schedule, and to work out a plan for tailored reminders (vibration, beep or LED light). The participants assigned to the control arm will be handed a Tel Me Box without

reminders. All will receive instructions on how the device works. See section 7.1.4 for details about the procedure. This will be handled by tech team staff, as the interviewers are blinded to what intervention arm the participant belongs to.

Interview general notes:

1. Total number of slots available for assessments is dependent upon the availability of assessment staff members and should not exceed 3 assessment interviews per assessment staff per day. E.g. if there are 5 assessment staff with full availability, the total number of slots available for that day is 15.
2. In the event that a potential participant drops in without any indication, or that a participant presents at a time other than the one for which s/he was scheduled, the assessment team will consult with the assessment coordinator or the study project manager (if the assessment coordinator is not available) to determine the most appropriate course of action. If the participant is within the interview window of the wave to be completed, and there is an assessment team member available who does not have 3 scheduled assessments that day, this interviewer will accommodate the participant and complete the assessment. If no assessment team member is available, or the participant is not within the window for a follow-up interview, a team member will try to convince the participant to come at the originally scheduled time, or reschedule for another date.

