2.4. Interview Procedures for 3m, 6m, 9m and 12m

Once the participant arrives at the site office, participant meets the tech team member first, to hand over the TMB device. The tech team member addresses any concerns with the device, and completes TMB related task as necessary (troubleshoot, SD card back up). Participant is then directed to the assessment team, where the interviewer will collect the study card. The study card is handed over to the data coordinator / data associate for verification.

Before administering the follow-up questionnaire, the interviewer will review tracking information with the participant to check if there are any changes in address and/or contact numbers since the last interview. If there are any changes in the tracking information a new tracking form will be filled. If there is no new information, the interviewer will make a note on the tracking form that the tracking form was reviewed and there are no changes.

After verifying and updating the tracking form, the interviewer will administer the follow-up interview the same way as outlined for the baseline questionnaire above. The 3 and 9 month follow-up visits, however, do not include blood sample collection. Hair sample collection is not to be included at 3, 6 and 9 month follow-up visits.

SECTION 3: FOLLOW-UP, TRACKING, AND WITHDRAWAL

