3.3.1. Conditions for Home and Workplace Tracking Visits for Participants Out of Contact

When the participant is not reachable over the phone (at least 10 attempts), has not responded to any messages on mobile or tracking through the ART centers, and the participant has failed to meet the interviewer for 15 days after the due date of the interview, the tracking team should plan a tracking visit.

The purpose of the visit is to get in touch with the participant and inform about the assessment follow-up date, time and venue. The team also should use this visit as opportunity to collect new contact details if they have changed. If the participant is willing and gives permission, the due assessment may be administered.

3.3.2. Conditions for Home and Work Place Visits for Assessment and/or to Exchange TMB

A home visit will be done in the following circumstances; (1) to complete a follow- up assessment when a participant reports his or her inability to come for the follow-up assessment interview and/or (2) to exchange a non-functional TMB when the participant is unable to come to the study

site. The assessment team will visit the home or appropriate place indicated in the tracking form at the discretion of the participant to complete the assessment, and/or TMB exchange. The following are examples of when a home visit will occur:

- *Ill health:* Participant is too ill to attend the assessment
- *Personal issues:* Participant reports personal issues that interfere with attending, such as depression, work, family functions, religious functions etc.
- *Financial issues:* Participant reports that he or she doesn't have money to travel to the assessment venue.
- *Transport related:* Participant reports that he or she has no transport available or very limited public transport services available to travel or has no transport available at the time the participant has to travel to the assessment venue.
- *TMB:* The TMB is not sending a signal or the participant has reported technical issues with the TMB and is unable to go to the study site for the exchange for the above reasons. Note: Any TMB-related visit needs to be conducted by a tech team member in order to keep assessment staff blinded to the assigned arm

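### Section 7.2.2 brings a female interviewer to device troubleshooting visits to women, which undercuts the protocol's own rule for keeping assessors blinded (minor, cheap to mend)

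*Protocol*

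**What the plan says.** The commitment to blinded assessors is explicit. Protocol 1.4 states: "The assessment team will be blinded to the allocation". Section 2.3.3 gives device hand-out to the technical team and says why: "This will be handled by tech team staff, as the interviewers are blinded to what intervention arm the participant belongs to". Section 3.3.2 extends this to the field: "Any TMB-related visit needs to be conducted by a tech team member in order to keep assessment staff blinded to the assigned arm". At follow-up visits on site, section 2.4 has a matching step, in which the "participant meets the tech team member first, to hand over the TMB device" and goes to the interviewer afterwards.

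Section 7.2.2 covers visits to repair boxes that have been offline for more than 48 hours despite telephone help. For men, the tech team coordinator sets up the visit. For women, that coordinator "contacts the Assessment Coordinator for help coordinating the visit, since it requires the presence of a female interviewer".

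Three other places touch the same subject:

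- Section 3.3.3, item 7, has a tech team member do any box exchange, but within the same home visit as the follow-up assessment.
- In section 3.3.2, one sentence has assessment staff, with no mention of technical staff, make the visit "at the discretion of the participant to complete the assessment, and/or TMB exchange". The closing paragraph of that section lets a study team member, with no team named, complete an exchange.
- Section 7.1.4 sends participants' questions at device hand-out to both the assessment and the tech coordinator each day, for discussion at both teams' meetings.

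**The concern.** The protocol treats contact between assessors and boxes as the way the blind could fail, and mostly keeps the two apart. Section 7.2.2 brings them together for one group of participants. Interviewers hold assigned participant IDs (2.3.2, 3.1), so the woman attending the repair visit could be the participant's own assessor, or become so later.

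The outcome at stake is self-reported adherence. Interviewers ask the questions in person (2.3.2, 2.4), and the SAP compares the answers between arms. An interviewer who knows the arm could, without intending to, affect how questions are put or how answers are probed. Device records, viral load and hair levels are much less open to this.

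**Working it through.** The plan states no figure on this point, so the check is mainly a comparison of passages.

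**1. Do the boxes differ by arm?** Yes, in function. Section 2.3.3 gives intervention boxes reminders by vibration, beep or light; section 7.1.4 gives control boxes none. Section 7.1.2 stocks the two kinds separately, so a replacement presumably has to match the arm. The documents do not say whether the two kinds look alike.

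**2. What happens at a troubleshooting visit?** Under 7.2.2 the tech team member checks the box, restarts it three times, inspects it for damage, and may change the SIM or the whole box. The interviewer does none of this. She is only required to be present.

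**3. Is she kept apart from the device work, or from that participant afterwards?** No such instruction appears in 7.2.2, 3.1 or 3.3. The offline and low-battery flowcharts and the supplementary guide mentioned in 7.2 are not in the available text, so a rule there cannot be excluded.

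**4. Is an interviewer needed?** Section 3.3.3, item 2, meets the same need at tracking visits to women by asking for a female team member, without naming a team. Section 7.2.1 has female team members make the troubleshooting calls to women, within calls assigned to tech team members. The specific demand for an interviewer is found only in 7.2.2.

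**5. Does the home-visit rule close the gap?** Only in part. Item 7 of 3.3.3 keeps the exchange in technical hands, but it sets no order and no separation, unlike the site routine in 2.4.

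**6. Can the effect be sized?** No. That would need the number of women, the rate of such visits, the chance that the interviewer learns the arm and later assesses the woman, and the shift *d* in a recorded answer when the arm is known. None is given.

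Only the leverage of one affected woman can be worked out, in units of the unknown *d*. Assume that self-report is measured at 0, 3, 6, 9 and 12 months, time is linear in the SAP's time-by-group model, all 60 participants per arm are retained, working independence holds, and *d* applies at every wave after exposure. The time deviations are −6, −3, 0, 3 and 6, with sum of squares 36 + 9 + 0 + 9 + 36 = 90. Her effect on the arm's fitted 12-month change is 12 × (sum of deviations at affected waves) / 90 / 60:

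- exposed before 3M: 12 × 6 / 90 / 60 = 1.33% of *d*
- after 3M: 12 × 9 / 90 / 60 = 2.0% of *d*
- after 6M: 12 × 9 / 90 / 60 = 2.0% of *d*
- after 9M: 12 × 6 / 90 / 60 = 1.33% of *d*

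Her share of the arm's 60 × 4 = 240 planned follow-up interviews would be the wrong yardstick, because the fitted contrast weights the waves unequally. Neither measure gives the size of the bias, since *d* and the number of women affected are unknown.

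**The case against.** The best defence is that presence is not exposure. The tech team member does the device work, the listed steps are the same for both arms, and nothing suggests that a reminder would sound during the visit. Participants know whether their box reminds them and could say so at any interview. The SAP calls these comparisons illustrative, and Aim 3 does not name self-report. All of this stands, and it keeps the point minor. It does not remove the mismatch between 7.2.2 and the stated purpose of the note in 3.3.2.

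A reader might infer three stronger things that the documents do not support:

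- *That assessors are in fact unblinded.* The text does not say whether the boxes look alike, which interviewer attends, or what she sees.
- *That section 3.3.2 has assessors exchange boxes.* One sentence, read alone, says so. The note in the same section, the opening of 3.3.3 (which gives device-related visits to the tech team) and item 7 of 3.3.3 show the contrary intent. The unnamed study team member is compatible with the note. This is loose wording, not a missing safeguard.
- *That section 7.1.4 passes allocation to interviewers.* A question about a reminder would reveal the arm only if it were linked to a participant. The text does not say that questions carry IDs, mention reminders, or are discussed case by case.

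**Conclusion.** The point holds as a minor gap in procedure. Section 7.2.2 requires an assessor at a device visit that the protocol elsewhere keeps technical in order to protect the blind, and no available text prevents her from assessing the same woman afterwards. Item 7 of section 3.3.3 leaves a similar opening at home visits. The requirement in 7.2.2 is stated for women whose box is offline for more than 48 hours, and should not be read as covering every participant.

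The likely consequence is slight and confined mainly to one of the SAP's four outcomes (device adherence, viral load, hair level, self-report). Its size cannot be estimated. The conclusion assumes that the flowcharts and guide outside the available text contain no rule of separation. The chief gain from acting is that a report of blinded assessors would match the procedures.

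**What to change.** **Main changes**

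- In 7.2.2, replace *female interviewer* with *female team member*, as in 3.3.3. She should come from the tech team where one is available; otherwise she should be an interviewer who does not hold that ID.
- Log her attendance, so that the ID is not given to her later under the monthly assignment in 3.1.
- In 3.3.3, item 7, when an exchange falls within an assessment home visit, complete the interview first and have the tech team member handle the box away from the interviewer.
- Log any known unblinding by ID and wave, and describe assessor blinding as partial if it occurs.

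**Secondary changes**

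- In 7.1.4, remove IDs and reminder content before hand-out questions reach assessment staff. This is a precaution only.
- In 3.3.2, bring the sentence on exchanges and the closing paragraph into line with the section's own note.

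**Cost.** The work is protocol wording and a short log. Scheduling becomes less flexible for visits due within 24 hours, attendance constrains later ID assignment, and assessment staff receive somewhat less feedback on the device. The documents do not give the number of women on each team. If no suitable woman is free, the visit goes ahead as now and the exposure is logged.

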7.3 Device Return for Withdrawn Participants

If a participant withdraws from the study and needs to return the device, the tech team member will collect the device and check if all the components are intact, especially SD card and sim card. If the device components are found to be damaged, record the damage in log maintained by tech engineer. Once the device is collected, the tech team member will hand over the device to the tech team coordinator. If the participant withdraws from the study but has not returned the device yet the ID will be added to the device tracking excel sheet on the daily logs. The tech team members will contact the withdrawn participant regularly and retrieve the device from the participant as soon as possible.

APPENDIX A: TMB TRACKING FORM

TMB Tracking form

Screener's Initials:		Interviewer / Counselor Initials:	
Participant Number:		Interview Date:	
Hospital No		ART No	
Name (Full):		Spouse's Name	
Father's Name:		Mother's Name	
Age:		Gender:	

Unique Identifier: (To identify participants when there are more than one participant

bearing same name) If the participant doesn't have an initial please assign an initial (First letter of participant's child's name, spouse's name etc. For eg: If the participants spouse's name starts with 'K' assign the same letter after the participant's name. Please let the participants know when you do this and tell him or her why you have to do this)

Initials	Initials taken from the name of								
	Spouse	Son	Daughter	Brother	Sister	Father	Mother	Friend	Others
									Specify

Contact numbers

Land		Mobile 1:	
------	--	-----------	--

line:			
Mobile 2:		Office:	

Address:

Conta ct perso n: (if any)	Name:	Relationship:	
		Contact No:	

Special identification /instructions:

House name:		Trade:	
Caste/Sub caste:		Ancestral name:	
Father's Name:		Others:	

Permissions (Check box if permission granted)			Instructions
Home visit	 Y	 N	
Work place visit	 Y	 N	
Tracking visit	 Y	 N	

Route map and Land marks: [Mandatory] *Please give reasons if participant doesn't want to provide: Route map includes transport route to be taken from a specified start point, route no (if any), destination, route from alighting point to the participant residence, work place and the land marks near the participants house such as coffee shop, temples, schools etc.*

Trial number: NCT03086655

Tel-Me-Box:

Testing a New, Real-time Strategies for Monitoring HIV Medication Adherence in India

Statistical analyses Plan:

This is a feasibility trial of automated reminders from an electronic pillbox (the Tel-Me-Box). Feasibility analyses will include tabulation of preference for the different kinds of reminder available. Further descriptive analyses will include calculation of enrollment and retention rates over the 12-month follow-up period.

To assess if tailored real-time adherence feedback via Tel-Me-Box shows potential to improve adherence, we will compare adherence from Tel-Me-Box (quarterly assessment for 12 months), as well as HIV viral loads, and hair ARV levels (both every 6 months) in the intervention (Tel-Me-Box with reminder) and control groups (Tel-Me-Box without a reminder). We will also compare self-reported adherence (assessed quarterly) between the 2 arms. Differences between the two groups in change in the outcomes over time will be assessed via the interaction between time and group in GEE linear or logistic regression models, for continuous and categorical versions of the outcome variables, respectively. Count variables will be analyzed via Poisson or negative binomial regression, depending on absence (Poisson) or presence (negative binomial) of overdispersion in the data distribution. Robust standard errors will be used in cases of deviation from normality in the linear regression models. *Note that these analyses are for illustration purposes only, as these were not the primary analyses this pilot study was powered for.*
